### **8.5. Duration of Hospitalisation**

Duration of hospitalisation will be calculated in days to 1 decimal place from time of informed consent to time of discharge, or time of last AE review if not discharged, and summarised using summary statistics for continuous data. CCI [REDACTED]

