8.4.4 Removal of Subjects from Therapy or Assessments

Subjects may be withdrawn from the study for any of the following reasons:

- Parent/legal guardian request
- Use of prohibited concomitant medication/therapy

- Non-compliance with the protocol
- Lost to follow-up
- Occurrence of AEs that are not compatible with the continuation of the subject in the study, in the Investigator's opinion, or that make it unacceptable to the subject's parent/legal guardian for them to continue
- Investigator request
- Intercurrent illness
- Sponsor request
- Becoming critically ill with respiratory insufficiency leading to the requirement for mechanical ventilation/positive airway pressure (PAP)/high-flow oxygen
- Randomisation code broken prematurely (Parts B and C)

Parents/legal guardians are free to withdraw their children from the study at any time without providing reason(s) for withdrawal and without prejudice for receiving further treatment. The reason(s) for withdrawal will be documented in the case report form (CRF). Parents/legal guardians who choose to withdraw their child from the study will be encouraged to allow their child to complete the same final evaluations as subjects completing the study according to the protocol, particularly safety evaluations.

All reasonable efforts should be made to contact the parent/legal guardian of a subject who is lost to follow-up. These efforts must be documented in the subject's file.

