1. A dose has been identified that fulfils the target PK profile.
2. Following review by the DSMC, safety at the selected dose is considered acceptable.
3. Sufficient antiviral effect has been identified to support the probability of an effect on the clinical manifestations of RSV infection.

Subjects will participate up to 13 days, and the visit schedule will include:

Screening Visit (-24 hours to first dose), Dosing Visit 1, Dosing Visit 2, Dosing Visit 3, Dosing Visit 4, Dosing Visit 5, Follow-Up 40-48 hours Post-Dose 10 (Visit Day 7) and a Telephone Follow-Up (Day 12).

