#### 3.6.2. Inclusion Criteria

To be eligible for study entry subjects must satisfy all of the following criteria at the Screening Visit:

1. Male or female  $\geq 1$  month and  $\leq 36$  months of age
2. Weigh  $\geq 3.5$  kg
3. Clinical diagnosis of LRTI defined by
  - a. Evidence of respiratory infection by one or both of the following with or without fever:
    - i. Rhinitis/coryza
    - ii. Cough  
AND
  - b. Evidence of LRTI by the presence of one or more of the following:
    - i. Increased respiratory rate PLUS other evidence of lower respiratory tract disease (e.g., laboratory or radiographic evidence)
    - ii. Increased respiratory effort as evidenced by one or more of the following:
      1. Grunting with expiration
      2. Nasal flaring
      3. Retraction: intercostal or subcostal
    - iii. Wheezing: audible or on chest auscultation
4. A positive RSV diagnostic test (RSV infection confirmed either according to routine site practice [polymerase chain reaction or diagnostic quick test], or using a [Sponsor-provided] commercial kit)
5. Hospitalised because of RSV LRTI (bronchiolitis or bronchopneumonia).

This document is confidential.

6. For Part B, symptoms of LRTI must be present for no more than 1 week before the Screening Visit, with the first day of symptoms counting as Day 1.
7. For Part C, symptoms of LRTI must be present for no more than 5 days prior to the Screening Visit, with the first day of symptoms counting as Day 1.
8. Expected to remain in hospital for a minimum of 3 days (administration of 6 doses for both Parts B and C)
9. The parent(s)/legal guardian(s) of the subject have provided written informed consent for the subject to participate
10. The parent(s)/legal guardian(s) are able and willing to comply with the study protocol

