## 6. General Aspects for Statistical Analysis

### 6.1. General Methods

- Unless otherwise specified, summaries for Part A will be presented by cohort, dose level and overall, summaries for Part B will be presented by cohort, treatment, dose level and overall, and summaries for Part C will be presented by treatment and overall.
- Unless otherwise specified, continuous variables will be summarised using the number of observations (n), mean, standard deviation (SD), median, minimum, and maximum. Means and medians will be presented with one more decimal than the observed values. SD values will be presented with 2 more decimals than the observed values.
- Unless otherwise stated, categorical variables will be summarised using number of observations (n), frequency and percentages of subjects.
- Presentations for PK data are described separately in Section 9. Presentations for PD data are described in Section 10.
- All relevant subject data will be included in listings. All subjects entered into the database will be included in subject data listings.
- All statistical testing will be 2-sided with an alpha level of 0.05, with no adjustment for multiple comparisons.
- For Part B, formal statistical testing will focus on the 24 subjects treated at the doses used in Cohort 5 that were identified in Cohorts 3 and 4. These 24 subjects comprise the whole of Cohort 5, plus the 4 subjects from each of Cohorts 3 and 4 that were randomized with the selected dose/placebo.
- Where there are multiple assessments at a given time point, only the results recorded on the scheduled time point page of the case report form (CRF) will be used for summarisation, unscheduled assessments will be listed only.

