## 8.3. RSV-related Signs and Symptoms

RSV-related signs and symptoms (temperature, respiratory rate, coryza, cough, grunting with expiration, nasal flaring, retractions, wheezing and SpO2 on Room air) will be collected on the CRF at each time point identified in the Schedule of Assessments for Part B (Table 2), and Part C (Table 3) in Section 3.10.

For study Parts B and C, assessments of individual RSV-related signs and symptoms will be summarised at each time point. For quantitative variables, observed values and changes from baseline will be summarised. In addition, highest level of severity during the study for each individual RSV-related sign and symptom will be summarised using summary statistics for categorical variables.

Time to improvement will be calculated for RSV-related signs and symptoms that are classified as moderate or severe during the course of the study and will be defined as the time from randomisation until no longer present (absent or severity=0) or mild. If there is no improvement, then time to improvement will be censored as the date/time RSV-related signs and symptoms were last recorded. Time to improvement will be summarised (number [%] of subjects analysed, mean, median, SD, minimum, maximum) for Parts B and C. The overall time to improvement will be defined as the time from randomisation to the time that all RSV-related signs and symptoms are mild or absent. The overall time to improvement will be summarised for Parts B and C by n, mean, median, SD, minimum, maximum and 95% confidence intervals for the mean. For Part C only, time to improvement of symptoms and overall time to improvement, will be compared between RV521 and Placebo using a Generalised Wilcoxon analysis, which is a weighted log-rank test, weighted by the number of subjects at risk immediately prior to the event, and will include duration of symptoms prior to randomisation as a covariate. Also for Part C only, Kaplan-Meier plots for time to improvement of symptoms and overall time to improvement will be presented by treatment.

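### In Parts A and B, SAP 8.5 enters the stay of an infant not yet discharged as if it had ended at the last AE review

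*SAP*

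**What the plan says.** SAP 8.5 runs the duration "from time of informed consent to time of discharge, or time of last AE review if not discharged, and summarised using summary statistics for continuous" variables. The text that follows in 8.5 is redacted. Under SAP 6.1, "continuous variables will be summarised using the number of observations (n), mean, standard deviation (SD), median, minimum, and maximum". The opening of SAP Section 8 keeps withdrawn infants in the summaries where possible.

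The SAP index lists Tables 14.2.5.1 and 14.2.5.2 (Parts A and B) as summary statistics. The entry after Table 14.2.5.2 is redacted. Figure 14.2.5.3.2 is a Kaplan-Meier plot of time to discharge, for Part C. The readable index has no matching figure for Parts A or B.

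The neighbouring variables in SAP 8.3 are built differently. Time to improvement "will be defined as the time from randomisation until no longer present (absent or severity=0) or mild". For both improvement and resolution, an infant without the event is censored at the last record.

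Two other passages bear on the point:
- Protocol 8.4.4 lists, among the reasons for withdrawal, "Becoming critically ill with respiratory insufficiency leading to the requirement for mechanical ventilation/positive airway pressure (PAP)/high-flow oxygen". After withdrawal, completing the final evaluations is encouraged but not assured.
- The Part B visit schedule in SAP 3.5 opens with "Screening Visit (-24 hours to first dose), Dosing Visit 1", and SAP 3.6.2 requires the infant to be in hospital already for RSV LRTI at screening.

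**The concern.** For an infant still in hospital, the time to last AE review is only a lower bound on the stay. Section 8.5 puts that lower bound into the mean, SD, median, minimum and maximum with no mark to separate it from a completed stay. The infants affected are not a random subset: those not discharged by their last review include the sickest, and critical illness is itself a listed reason for leaving the study.

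The start point raises a lesser question. Infants are in hospital before consent, so the variable is not the hospital stay. Consent comes before randomisation, so it is not time from randomisation either.

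What is at stake is the reading of a small descriptive table, above all in Part B, where RV521 and placebo columns will be compared by eye.

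**Working it through.** The documents give no sample size, power or target value for this variable, so there is no planned figure to reproduce. The check works out which values the rule can produce and how far one incomplete stay can move a mean.

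**1. Undischarged infant followed to the last scheduled AE review.** Protocol 10.1.3.1 puts this at Day 7 after dosing in Part A and Day 12 in Part B. Consent is up to about 1 day before the first dose.
- Part A: 7 + (0 to 1) = about 7 to 8 days.
- Part B: (12 − 1) + (0 to 1) = about 11 to 12 days.

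These are long values. They still understate the stay, because the infant has not gone home.

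**2. Undischarged infant whose AE review stops early.** If the infant leaves the study at about Day 2 and is not reviewed again, the recorded duration is about 1 to 2 days. That is below the 3-day minimum stay expected for Part B in SAP 3.6.2.

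**3. Effect on an arm mean.** Let *k* infants in an arm of *n* have true stay *T* but be closed at *w* days. The error in the mean is −*k*(*T* − *w*)/*n*. The documents do not give *T*, *w* or *k*. Assume *T* = 7 to 14 days, *w* = 1 to 2 days and *k* = 1. The arm sizes are the 2:1 split of 24 in Part B.

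| Arm | Smallest error | Largest error |
|---|---|---|
| Placebo, n = 8 | −(7 − 2)/8 = −0.62 days | −(14 − 1)/8 = −1.62 days |
| RV521, n = 16 | −(7 − 2)/16 = −0.31 days | −(14 − 1)/16 = −0.81 days |

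**4. Worked example, all values assumed.** Eight infants: seven discharged at 3, 3.5, 4, 4, 4.5, 5 and 6 days (sum 30), and one withdrawn for ventilation at 1.5 days with a true stay of 10.
- As written: mean (30 + 1.5)/8 = 3.94, median 4.0, and the ventilated infant is the minimum.
- With the true stay: mean (30 + 10)/8 = 5.00, median 4.25, and the same infant is the maximum.

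The median hardly moves. The mean and the extremes do.

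**5. Whether plain censoring is enough.** In the same example, censoring the eighth infant at 1.5 days leaves seven at risk, all discharged by day 6. The Kaplan-Meier curve then shows 100% discharged by day 6. Counting the infant as not discharged gives 7/8 = 87.5%. Censoring at an exit caused by deterioration is informative and hides the poor outcome.

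**6. Origin.** Starting at consent omits the whole pre-consent stay, whose length the documents do not give, and includes up to about 24 hours before Dose 1.

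**The case against.** The strongest reply is that the rule usually does not make sick infants look well. The clock stops at the last AE review, not at withdrawal, and several provisions keep review going. An event that prolongs hospitalisation or is life-threatening is an SAE. Protocol 10.1.3.1 asks for follow-up until events resolve or stabilise, and for subjects to be followed to the last follow-up visit. Protocol 8.4.4 encourages final evaluations after withdrawal, safety evaluations in particular. This stands. A reader might infer that the longest stays are generally recorded as the shortest, and the documents do not support that: an undischarged infant kept under review receives one of the longest values. The reversal needs an early end to AE review, which is possible but not the expected course.

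The origin can also be defended. Consent exists in all three Parts, Part A has no randomisation, and time before randomisation cannot be affected by treatment and should balance in expectation. That makes the origin a minor point, although a figure labelled as hospitalisation should still say what it measures.

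Finally, the variable is not a primary or secondary endpoint in the readable text for Parts A and B, and no test or model is attached to it there. Part A has a single treatment, so no comparison with placebo can be distorted. All of this limits the consequence. It does not make an incomplete stay a complete one.

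**Conclusion.** The point holds for Parts A and B. SAP 8.5 treats an open stay as closed, which always understates the stay of an infant still in hospital. Where AE review ends early, through withdrawal for deterioration or death, it can record a short stay for a very sick infant. On the assumed stays, one such infant costs an arm mean about 0.6 to 1.6 days at n = 8 and 0.3 to 0.8 days at n = 16. These ranges rest on *T*, *w* and *k*, none of which is in the documents, so they illustrate size and do not predict it.

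Two further inferences should be resisted. A reader might conclude that Part C also lacks censoring. A Kaplan-Meier plot of time to discharge is listed for it and adjacent text is redacted, so nothing can be said against its handling. A reader might also conclude that the trial's power or error rate suffers, but no such figure depends on this variable.

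**What to change.** Amend SAP 8.5 for Parts A and B as follows:
- Define time to discharge from randomisation in Part B, matching SAP 8.3, and from first dose in Part A.
- Treat an infant not discharged as censored at the last known inpatient status, not as a completed stay.
- Carry an in-hospital death, or a withdrawal for deterioration, as not discharged through the end of scheduled follow-up (Day 7 in Part A, Day 12 in Part B), because censoring at exit would be informative.
- Report the number not discharged by arm (by dose group in Part A), with Kaplan-Meier estimates. The median alone is not enough, since it barely moves in the example above.
- Label any figure that starts at consent as time from consent, not as total hospital stay. Total stay would need an admission time, which is not among the screening items listed in protocol 9.1.1.

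The cost is a short SAP revision and a little programming for a descriptive variable. Discharge, randomisation and dosing times are already used in the SAP. Sample size and alpha are unaffected.

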### **8.6. Hydration Status**

For each of Parts A, B and C, dehydration will be recorded as:

- None.
- Mild 3-5%.
- Moderate 6-10%.
- Severe >10-15%.

The number and percentage of subjects with none, mild, moderate and severe dehydration will be summarised at baseline and at each post-baseline time point.

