11.1.1 Datasets or Populations Analysed

The study populations include the Safety Population, PK Population, PD Population, and Efficacy Population.

Safety Population: defined as all subjects who received a single dose (Part A) or any part of any multiple dosing regimens (Parts B and C) of IMP (RV521 or placebo). The Safety Population is the primary population for the analysis of safety data. Analysis will be according to actual treatment received.

PK Population: defined as all subjects who receive IMP and have at least 1 post-dose PK concentration measured. The PK Population is the primary population for the analysis of PK data. Analysis will be according to actual treatment received.

Modified Intent-to-Treat (mITT) Population

The mITT Population is the primary population for the analysis of efficacy and PD data. Subjects will be analysed according to the randomised treatment. The mITT Population is defined as follows:

- In Part A, the mITT is defined as all subjects enrolled in the study who have an RT-qPCR viral load measurement and/or CBIA, if available, for at least 1 time point including baseline: pre-dose at Dosing Visit 1.
- In Part B, the mITT Population will include all subjects who received at least one dose of IMP (RV521 or placebo) and have a pre-treatment positive RSV nasopharyngeal swab confirmed by the central laboratory and agreed by the project team during the blind data review meeting. Potential inclusion of subjects who have not completed at least 6 doses of IMP will be decided by the project team during the blind data review meeting. Subjects will be analysed according to the randomised treatment.
- In Part C, the mITT Population will include all subjects who received at least one dose of IMP and have a pre-treatment positive RSV confirmed by the central laboratory.

Demographic and Other Baseline Characteristics: Demographic and baseline characteristics will be summarised descriptively by treatment. Quantitative variables will be summarised using the statistics n (number of observations), mean, standard deviation, median, minimum and

maximum. Qualitative variables will be summarised using n (number of subjects), absolute numbers and relative frequencies (%) per class.

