## 5. Analysis Populations

### 5.1. Safety Population

The Safety Population will include all subjects who received at least 1 dose of IMP (RV521 or placebo). The Safety Population is the primary population for the analysis of safety data. Analysis will be according to actual treatment received.

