### 5.2. mITT Population

The Modified Intent-to-Treat (mITT) Population in Part A will include all subjects enrolled in the study who have an RT-qPCR viral load measurement and/or CBIA, if available, for at least 1 time point including baseline pre-dose at Dosing Visit 1.

The mITT Population in Parts B and C will include all subjects who received at least 1 dose of IMP (RV521 or placebo) and have a pre-treatment positive RSV nasopharyngeal swab confirmed by the central laboratory and agreed by the project team during blind data review meeting. Potential inclusion of subjects who have not completed at least 6 doses of IMP will be decided by the project team during blind data review meeting.

Subjects will be analysed according to randomised treatment. The mITT Population is the primary population for the analysis of efficacy and PD data.

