## 8. Clinical Efficacy

All summaries and analyses of clinical efficacy data will be based on observed data in the mITT Population. No imputation of missing data will be done and there will be no adjustments for multiplicity. Data from subjects who withdraw will be included, where possible, in all summaries and analyses.

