## 12. Safety

The population used for safety analyses will be the Safety Population. Safety will be assessed on the basis of AE reports, clinical laboratory data, ECG parameters, physical examinations, and vital signs.

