	14.2.4.1.2	Part A: Supplemental Oxygen Use: Duration and Maximum Level : Summary Statistics	mITT Population

This document is confidential.

Header	Table Number	Name	Analysis Population
	14.2.4.2.1	Part B: Supplemental Oxygen Use: Summary Statistics	mITT Population
	14.2.4.2.2	Part B: Supplemental Oxygen Use: Duration and Maximum Level : Summary Statistics	mITT Population
	14.2.4.3.1	Part C: Supplemental Oxygen Use: Summary Statistics	mITT Population
	14.2.4.3.2	Part C: Supplemental Oxygen Use: Duration and Maximum Level : Summary Statistics	mITT Population
14.2.5		Duration of Hospitalisation	
	14.2.5.1	Part A: Duration of Hospitalisation: Summary Statistics	mITT Population
	14.2.5.2	Part B: Duration of Hospitalisation: Summary Statistics	mITT Population
	CCI		
14.2.6		Hydration Status	
	14.2.6.1	Part A: Hydration Status: Summary Statistics	mITT Population
	14.2.6.2	Part B: Hydration Status: Summary Statistics	mITT Population
	14.2.6.3	Part C: Hydration Status: Summary Statistics	mITT Population
14.2.7		Pharmacokinetics	
14.2.7.1		Plasma Concentration Data	
	14.2.7.1.1.1	Part A: Plasma RV521 Concentrations	PK Population
	14.2.7.1.2.1	Part B: Plasma RV521 Concentrations	PK Population
	14.2.7.1.3.1	Part C: Plasma RV521 Concentrations	PK Population
14.2.7.2		Pharmacokinetic Parameters	
	14.2.7.2.1	Part A: Pharmacokinetic Parameters	PK Population
	14.2.7.2.2	Part B: Pharmacokinetic Parameters	PK Population
	14.2.7.2.3	Part C: Pharmacokinetic Parameters	PK Population
14.2.8		Pharmacodynamics	
	14.2.8.1.1.1	Part A: Log10 Total RSV Viral Load by RT-qPCR: Summary Statistics	mITT Population

This document is confidential.

Header	Table Number	Name	Analysis Population
	14.2.8.1.2.1	Part A: Log10 RSV Viral Load by CBIA: Summary Statistics	mITT Population
	CCI		
	14.2.8.2.1.1.1	Part B: Log10 Total RSV Viral Load by RT-qPCR: Summary Statistics	mITT Population
	14.2.8.2.1.2.1	Part B: Log10 RSV Viral Load by CBIA: Summary Statistics	mITT Population
	14.2.8.2.2.1	Part B: Total RSV Viral Load by RT-qPCR: DAVG by Incidence of Other Known Respiratory Pathogens at Baseline	mITT Population
	14.2.8.2.2.2	Part B: Total RSV Viral Load by RT-qPCR: DAVG Mixed Effects Analysis of Covariance	mITT Population
	14.2.8.2.2.3	Part B: RSV Viral Load by CBIA: DAVG by Incidence of Other Known Respiratory Pathogens at Baseline	mITT Population
	14.2.8.2.2.4	Part B: RSV Viral Load by CBIA: DAVG Mixed Effects Analysis of Covariance	mITT Population

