	14.3.4.1.3.2.3	Part B: Urinalysis: Abnormal Results by Study Visit	Safety Population
	14.3.4.1.3.3.1	Part C: Urinalysis: Summary of Continuous Results by Visit and Change from Baseline	Safety Population

This document is confidential.

Header	Table Number	Name	Analysis Population
	14.3.4.1.3.3.2	Part C: Urinalysis: Summary of Categorical Results by Visit	Safety Population
	14.3.4.1.3.3.3	Part C: Urinalysis: Abnormal Results by Study Visit	Safety Population
	14.3.4.1.3.4	Urinalysis: Abnormal Results, Listing	Safety Population
14.3.4.2		Vital Signs	
	14.3.4.2.1.1	Part A: Vital Signs	Safety Population
	14.3.4.2.1.2	Part A: Vital Signs Investigator Interpretation	Safety Population
	14.3.4.2.2.1	Part B: Vital Signs	Safety Population
	14.3.4.2.2.2	Part B: Vital Signs Investigator Interpretation	Safety Population
	14.3.4.2.2.3	Part B: Height, Weight, BMI and Head Circumference	Safety Population
	14.3.4.2.3.1	Part C: Vital Signs	Safety Population
	14.3.4.2.3.2	Part C: Vital Signs Investigator Interpretation	Safety Population
	14.3.4.2.3.3	Part C: Height, Weight, BMI and Head Circumference	Safety Population
14.3.4.3		ECG Data	
	14.3.4.3.1.1	Part A: Summary of Overall ECG Interpretation	Safety Population
	14.3.4.3.1.2	Part A: ECG Summary by Time Point and Change from Baseline	Safety Population
	14.3.4.3.2.1	Part B: Summary of Overall ECG Interpretation	Safety Population
	14.3.4.3.2.2	Part B: ECG Summary by Time Point and Change from Baseline	Safety Population
	14.3.4.3.3.1	Part C: Summary of Overall ECG Interpretation	Safety Population
	14.3.4.3.3.2	Part C: ECG Summary by Time Point and Change from Baseline	Safety Population
14.3.4.4		Physical Examination Results	
	14.3.4.4.1	Part A: Abnormal Physical Examination Results	Safety Population
	14.3.4.4.2	Part B: Abnormal Physical Examination Results	Safety Population
	14.3.4.4.3	Part C: Abnormal Physical Examination Results	Safety Population
14.3.4.5		Extent of Exposure	
	14.3.4.5.1.1	Part A: Extent of Exposure	Safety Population
	14.3.4.5.1.2	Part A: Extent of Exposure	mITT Population
	14.3.4.5.1.3	Part A: Extent of Exposure	PK Population
	14.3.4.5.2.1	Part B: Extent of Exposure	Safety Population
	14.3.4.5.2.2	Part B: Extent of Exposure	mITT Population

This document is confidential.

[figure not shown]

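### Hydration status, which the protocol treats as a safety assessment, is tabulated only in the mITT Population as randomised, so dosed infants in Parts B and C can be missing from its only table

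*SAP*

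**What the plan says.** **Protocol.** Hydration status is described in 10.1.3.10 (Other Evaluations), inside 10.1.3 (Safety Assessments). Appendix 17.5 labels the dehydration scale as belonging to the physical examination. The one-line list that opens 10.1.3 names physical examination but not hydration. The clinical response sections (10.1.2.2 and 11.1.5) do not mention hydration.

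**SAP, hydration.** Section 8.6 states: "The number and percentage of subjects with none, mild, moderate and severe dehydration will be summarised at baseline and at each post-baseline time point". It sits in Section 8, Clinical Efficacy, where "All summaries and analyses of clinical efficacy data will be based on observed data in the mITT Population". The Index of Tables agrees: Table 14.2.6.2, "Part B: Hydration Status: Summary Statistics", and its Part A and Part C counterparts are all assigned to the mITT Population. SAP 5.2 analyses that population by randomised treatment.

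**SAP, safety.** Section 12 states: "The population used for safety analyses will be the Safety Population". Section 5.1 says the same ("The Safety Population is the primary population for the analysis of safety data") and defines that population as every dosed subject, analysed by treatment actually received. Table 14.3.4.4.2, "Part B: Abnormal Physical Examination Results", follows this rule.

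**The concern.** The SAP's rule is that safety data are summarised for everyone dosed, as treated. Hydration departs from that rule only because of the section it was placed in. The examination that the protocol says contains the hydration grade is tabulated in the Safety Population; the grade itself is not.

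This matters because safety and tolerability is the primary objective of Part B and a secondary objective of Part C, and Protocol 6.6 lists vomiting and diarrhoea among the expected toxicities. One route out of the Part B mITT depends on how many doses were completed, which is a post-baseline event. An infant who stopped dosing early because of vomiting could fall under that rule and be absent from the table in which dehydration would be looked for.

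**Working it through.** There is no planned figure to reproduce. The check compares the two populations and then counts what else is measured.

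**1. Can the populations differ?**

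- *Central confirmation (Parts B and C).* Inclusion criterion 4 (Protocol 8.4.2) lets an infant enter on a site test or a commercial kit. The mITT then requires a central-laboratory positive: SAP 5.2 for Parts B and C and, in the current protocol for Part C, infants who "received at least one dose of IMP and have a pre-treatment positive RSV confirmed by the central laboratory". SAP 7.4 already plans to flag cases where the site and central results disagree.
- *Six doses (Part B).* SAP 5.2: "Potential inclusion of subjects who have not completed at least 6 doses of IMP will be decided by the project team", at the blind data review meeting. Protocol 11.1.1 has the same provision for Part B. SAP 15 explains that it was added because infants may fail to ingest doses yet stay in the study. Protocol 8.4.5 also anticipates infants who do not complete 6 doses.
- *Part C.* SAP 5.2 extends the six-dose provision to Part C; the current Protocol 11.1.1 does not. Central confirmation alone can still remove a dosed infant.
- *Part A.* Its mITT depends on having a viral load measurement, not on these rules. The argument does not rely on Part A.

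So, for Parts B and C:

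mITT = Safety Population − (dosed, not centrally confirmed) − (fewer than 6 doses and not admitted at blind review, where that rule applies).

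The mITT is therefore contained in the Safety Population and equals it only if both subtracted groups are empty.

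**2. What happens to an excluded infant?** SAP 17.2.5.2 sets the denominator as subjects in the analysis set with an observation. An infant outside the mITT is therefore dropped from numerator and denominator at every time point, and the table itself does not show the loss.

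**3. Do other tables cover it?** Scheduled time points after Dose 1, counted from Protocol Table 2 (Part B) and Table 3a (Part C inpatients):

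| Assessment | Part B | Of which only if in hospital | Part C (Table 3a) |
|---|---|---|---|
| Hydration | pre-Dose 3, 5, 7, 9, Day 7 = 5 | 2 (pre-Dose 7, 9) | 5 |
| Physical examination | Day 7 = 1 | 0 | 1 |
| Weight | Day 7 = 1 | 0 | Day 7, 14, 34 = 3 |
| Safety laboratory | Day 7 = 1 | 0 | 1 |
| ECG | post-Dose 1, pre-Dose 3, pre-Dose 5, post-Dose 6, pre-Dose 8, pre-Dose 10, Day 7 = 7 | 2 (pre-Dose 8, 10) | – |
| Vital signs | post-Dose 1, pre-Dose 2 to 6 (5), post-Dose 6, pre-Dose 7 to 10 (4), Day 7 = 12 | 4 (pre-Dose 7 to 10) | – |

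A Part B infant discharged after Dosing Visit 3 still has 5 − 2 = 3 scheduled hydration grades, against one each for physical examination, weight and safety laboratory tests. Vital signs and ECG are measured more often and are tabulated in the Safety Population, but they reflect hydration only indirectly. The Safety Population physical examination summary (SAP 12.7) is by body system and does not name the hydration grade.

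**The case against.** **Classification.** The opening list in Protocol 10.1.3 omits hydration, as do the safety endpoint lists and the opening of SAP Section 12. Hydration also reflects the RSV illness: the ReSVinet clinician scale scores feeding intolerance partly by whether hydration can be maintained. A clinical efficacy table is therefore defensible. This stands as a reason to keep the mITT table. It does not justify having no Safety Population table for an evaluation that the protocol places within Safety Assessments and calls part of a named safety examination.

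**Safeguards.** Listing 16.2.6.6 gives hydration for all subjects. SAP 7.1 summarises exclusions by reason. Dehydration, vomiting or diarrhoea reported as adverse events enter the Safety Population TEAE tables, and concomitant medication, weight, laboratory results and vital signs are tabulated there too. For Part B the DSMC receives data and listings with the randomisation list (Protocol 8.5.5), although whether hydration is among them depends on a charter that is not available here. In a Part B of 24 to 40 infants, a few listed records could be read by hand. All of this lowers the stakes, but none of it tabulates the scheduled grade by arm for every dosed infant.

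**No demonstrated bias.** Inclusion is decided blind, the rules cover all arms, and failing to ingest doses need not mean intolerance. The difference between treatment as randomised and as received matters only if an infant receives the wrong treatment. This is correct, and no direction of effect is claimed.

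**Outdated Part C text.** The SAP predates the current Part C design and must be revised anyway. That makes the correction cheap; central confirmation can still exclude dosed infants under the current protocol.

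**Conclusion.** The point holds. The only planned table of the scheduled hydration grade uses a population from which dosed infants in Parts B and C can be absent, contrary to the SAP's own rule for safety analyses.

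The size and direction of any effect are unknown, because neither a dehydration rate nor an mITT exclusion rate is given. If every dosed infant meets the mITT criteria and is treated as randomised, the two versions of the table are identical.

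The conclusion rests on reading Protocol 10.1.3.10 and Appendix 17.5 as making hydration a safety assessment despite its absence from the opening list of 10.1.3. It is an inexpensive improvement and does not threaten a primary conclusion.

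**What to change.** Add to SAP Section 12, for Parts B and C: *Hydration status (none, mild, moderate, severe) will be tabulated at baseline and each later scheduled time point in the Safety Population, by treatment received.* Index the matching tables, and keep the mITT versions as a supplement because hydration also tracks the illness.

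Two optional additions are a shift table from baseline to worst post-dose category, on the pattern of the laboratory grades in SAP 12.4, and the same Safety Population table for Part A.

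The cost is SAP wording, a small amount of reprogramming and a few extra tables, with no new data. Protocol 11.1 allows SAP amendments for Parts B and C before database lock and unblinding of each part. The SAP still describes a 1:1 Part C (3.5) and needs amending for the current 1:1:1 design anyway.
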